The objective of this study is to assess the feasibility and acceptability of an SSI (i.e., SPYKids) for parents on local Manitoban service and program waitlists who have children with health, behavioural, and developmental needs. This objective will be divided into Primary and Secondary outcomes.

1. Primary Outcomes: [FEASIBILITY & ACCEPTABILITY]:

Primary outcomes are aimed at determining the feasibility and acceptability of SPYKids compared to SAU. This will be done through monitoring of both clinical coach adherence to protocols via a fidelity checklist and parent satisfaction of the overall SSI via feedback questionnaires including both scaled responses and open-ended responses, using both quantitative and qualitative methodology. Parent feedback of the SSI will be assessed using the Program Feedback Scale²⁰ (adapted from [name] research), and the feedback questionnaire, which was created by researchers in the lab for the purposes of this study. Please see the attached Appendix C for all questionnaires.

2. Secondary Outcomes:

Secondary outcomes include metrics of parenting stress and mental health between the SPYKids and SAU groups before and after the SPYKids session. Other exploratory outcomes will include both parent and child well-being.

- Parent well-being: Secondary outcomes related to parent well-being will be changes in parenting stress (Parenting Stress Index²¹) and parent mental health

(Patient Health Questionnaire-9²², Generalized Anxiety Disorder – 7 item scale²³, PROMIS Anger - Short Form²⁴). Exploratory outcomes include changes in hope (Beck Hopelessness Scale-4²⁵), Perceived control/agency²⁶, Readiness to change (Readiness Ruler²⁷), and Problem Solving²⁶.

- Child well-being: Primary analyses will compare changes in child well-being scores (Strengths & Difficulties Questionnaire²⁸) between the SPYKids vs SAU groups. Secondary analyses will examine persistence of these effects at the 3-month follow-up.

Research Methods

Participants

We plan to recruit 70-140 participants and hope to randomize 70 participants to either the SAU or SSI groups (n= 35 per condition). In order to be eligible to participate, they must have a residence in Manitoba, be at least 18 years old, must identify as a primary caregiver to a child who is 2-5 years old, and the child must be on a waitlist for Neurodevelopmental Services in Manitoba (See Eligibility Screener in Appendix C).

Design & Study Procedures

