The time commitment is approximately 3 hours for the SSI program group, and 1 hour for the SAU group. Participants in the SSI group will fill out a brief online screener (2 minutes), a pre-session questionnaire (30 minutes), attend the 90-minute single session, fill out a post-session questionnaire (15 minutes), and then the two follow-up surveys (20 minutes each). Participants in the SAU group will also complete the brief online screener (2 minutes) and the pre-session questionnaire (30 minutes). After randomization, they will only complete the two follow-up surveys (20 minutes each).

Honorarium. Participants in both groups will receive up to \$75 in Amazon e-gift cards for their participation. Participants will be compensated at certain steps of the research project following the SSI (or pre-questionnaires for the SAU group) to encourage continued interest and participation, given that the project takes place over a longer period of time, and to compensate already busy parents for their time. Notably this compensation is designed to compensate time for assessments (questionnaires) only, but not the intervention time. Due to randomization both the SAU and the SSI group will receive the same \$75 compensation in the form of e-gift cards for participating. Participants in the SSI group condition will receive \$25 e-gift cards after taking the following questionnaires: the post-session questionnaires (which follows the pre-session questionnaires and SSI Zoom session) and after each of the two follow-up questionnaires (at 2 weeks and 3 months after the session). Participants in the SAU condition will complete the pre-questionnaire and after randomization will receive a \$25 dollar e-gift card to parallel the \$25 e-gift card received by the SSI group. Consistent with the SSI group, they will receive a \$25 e-gift card after each follow up questionnaire is completed (1 month and 3 months after pre-questionnaire) for a total of up to \$75 gift card for participating.

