Across all self-report questionnaire outcomes, measures have excellent reliability and validity. This includes established cut-offs indicating mental health problem severity needs therapeutic services with high sensitivity/specificity to diagnostic interviews. Constructs with established tools from consortium agreements, per the COMET (Core Outcome Measures in Effectiveness Trials) Initiative are prioritized.²⁹

Primary outcome. Child mental health. The primary analyses will compare the change in child mental health symptom scores between (a) the SPYKids vs SAU group at $p=0.05$ using a linear model for the change, accounting for pre-intervention scores and important covariate of child age. Secondary analyses will examine persistence of these effects at the 3-month-follow-up by examining the time-by-intervention interactions in a linear mixed-effects model accounting for within-subject serial correlations, and between-subject effects of the intervention and age.

Secondary outcomes. Parenting stress & mental health. We will use similar linear mixed-effects models for the analysis of key secondary outcomes.

Exploratory outcomes. Parent Self-Efficacy. Exploratory analyses (SPYKids only) will assess the extent to which dimensions of parenting self-efficacy (hope,²⁵ agency,²⁶ readiness to change²⁷) immediately following the intervention are associated with primary and secondary change. This will inform how immediate post-treatment progress is linked to subsequent improvements in well-being. Parent Satisfaction will be assessed to determine if key benchmark

acceptability is met 3.5/5 on an established scale.²⁰ Participants will complete open-ended text-based items allowing them to express their views on the intervention content, their engagement with this content, their satisfaction with their involvement in the intervention, and suggested improvements. Open-ended text items will be analyzed using thematic analysis.³⁰

General considerations. In general, p-values < .05 will be considered statistically significant, without controlling for multiple inference. Complete-case methods will be used for planned analyses; however, sensitivity analyses may be used to examine the impacts of imputation on conclusions, should the usual assumptions appear to be met (MAR, missing at random, or MCAR, missing completely at random). Data will be stored in REDCap following Good Clinical Practices.³¹ Analyses will be done in R v.4.0.0 and the lme4 package v 1.1-26.35

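### The exploratory self-efficacy analysis is read as showing progress, but as written its predictor is a post-session level with no pre-session score of the same measure

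*Combined protocol and SAP*

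**What the plan says.** The analysis is set out in Statistical Analyses, under Exploratory outcomes: "Exploratory analyses (SPYKids only) will assess the extent to which dimensions of parenting self-efficacy", namely hope, agency and readiness to change, "immediately following the intervention are associated with primary and secondary change. This will inform how immediate post-treatment progress is linked to subsequent improvements". The first sentence of that last quotation names the predictor's timing; the second gives the interpretation. No model, change score or baseline covariate is stated for these predictors.

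Three other places bear on the point:

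- The primary child mental health model in the same section does name a baseline adjustment, "using a linear model for the change, accounting for pre-intervention scores and important covariate of child age". That wording belongs to the child outcome, not to the self-efficacy predictors.
- Aims and Hypotheses, under Secondary Outcomes, lists the same constructs as outcomes: "Exploratory outcomes include changes in hope", followed by perceived control/agency and readiness to change.
- Further Details on Project Components describes what parents in the intervention group complete: "a pre-session questionnaire (30 minutes), attend the 90-minute single session, fill out a post-session questionnaire (15 minutes" in length. A pre-session score is therefore probably collected. The table of questionnaires is in Appendix C, which is not in the text supplied.

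**The concern.** The predictor is a state at one time point and the conclusion is about change. A parent who arrived hopeful and did not move scores the same after the session as one who arrived discouraged and moved a long way. If parents who start more hopeful or ready also tend to improve more later, the post-session score will be associated with later improvement even when the session moved nobody in a way that mattered.

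The result would then be reported as early progress carrying through to later well-being, when it shows only that starting point predicts course. There is no control arm in this analysis to expose that, and the plan uses p < .05 without multiplicity control. What is at stake is the interpretation of one exploratory finding.

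**Working it through.** The plan gives no effect size, correlation or power for this analysis, so there is no figure of its own to reproduce.

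**Inputs from the documents.** At most 35 parents (intervention group, complete cases) and a 0.05 threshold. Sidedness is not stated; two-sided is assumed.

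**Inputs assumed.** r is the correlation of pre- with post-session score, and rho is the correlation of the pre-session score with later change in the outcome. Both are oriented so that higher means better. Pre and post variances are equal. Reliability is also assumed: the plan says "Across all self-report questionnaire outcomes, measures have excellent reliability and validity" but gives no coefficient.

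**Step 1: how much of the post-session level is movement.** With equal variances, corr(post, post − pre) = (1 − r)/√(2(1 − r)) = √((1 − r)/2).

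- r = 0.5: √0.25 = 0.50
- r = 0.7: √0.15 = 0.39
- r = 0.8: √0.10 = 0.32

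The level is only a weak to moderate stand-in for progress.

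**Step 2: what happens when progress has no relation to later change.** Later change is made to depend on the pre-session score alone. The post-session score then correlates r × rho with later change, for example 0.7 × 0.3 = 0.21 or 0.8 × 0.5 = 0.40. Proportion of simulated trials significant at 0.05 (n = 35, 40,000 runs per row, error-free measures):

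| r | rho | Post score alone | Post score with pre score | Raw change |
|---|---|---|---|---|
| any tested | 0 | about 5% | about 5% | about 5% |
| 0.7 | 0.1 | 7% | 5% | 5–6% |
| 0.5 | 0.2 | 9% | 5% | 9% |
| 0.7 | 0.3 | 23% | 5% | 10% |
| 0.8 | 0.5 | 68% | 5% | 15% |

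**Step 3: sign.** At r = 0.7, rho = −0.3, the post score alone is still significant in 23% of trials, but only 0.1% of trials give a significant positive association. A spurious negative association would not be read as progress linked to improvement, so the stated harm needs rho > 0.

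**Step 4: measurement error.** The adjusted coefficient then has bias r × rho × (1/rel − 1)/(1 − r²), which takes the sign of rho. The raw-change coefficient has bias −rho × (1 − r/rel)/(2(1 − r)), which has the opposite sign as long as reliability (rel) exceeds r. At r = 0.7, reliability 0.8, with rho 0.3 to 0.4:

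- post score alone: 34–55% significant
- with the pre score: 7–9%
- raw change: 6–7%

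Adjustment removes most of the excess, not all of it.

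**Step 5: cost in precision and power (n = 35, r = 0.7, error-free).** The standard error widens by about 1/√(1 − r²) = 1/√0.51 = 1.40.

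- If residual progress correlates 0.4 with later change and rho = 0, power rises from 39% (post alone) to 67% (adjusted).
- If the post-session level itself is what correlates 0.4 with later change, the pre score correlates 0.7 × 0.4 = 0.28. The partial correlation is (0.4 − 0.7 × 0.28)/√((1 − 0.49)(1 − 0.0784)) = 0.204/0.686 = 0.30, and power falls from 68% to 41%.

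**The case against.** The best reply is that change is what the investigators mean. The interpretive sentence uses change language, the Secondary Outcomes list speaks of changes in these constructs, and intervention parents complete questionnaires before and after the session. The exploratory paragraph specifies no model at all, so a reader who infers that the wrong predictor was deliberately chosen goes further than the text does. That part of the reply stands: the defect is that the predictor is not specified as change. It does not close the matter, because the Secondary Outcomes list defines outcomes and not this predictor. Someone following the exploratory paragraph literally would fit the post-session score alone.

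A reader might also infer that pre-session scores are not collected. The documents do not support that. They point the other way, and Appendix C would settle it.

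Further points stand in part. Every size above rests on assumed inputs, and the excess vanishes if r or rho is zero. Whether post-session level predicts later change is a legitimate question in its own right. The plan's verbs are modest, speaking of association and of informing. The objection that the analysis is only exploratory is correct and limits the severity; it does not make level and progress the same thing.

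**Conclusion.** The point holds as one of specification and wording. Read as written, the analysis relates a post-session level to later change and cannot by itself support a statement about progress. Under the assumptions shown (35 parents, error-free measures, progress unrelated to outcome, rho ≥ 0), the post-session score alone is significant in about 5% of trials at rho = 0, 23% at r = 0.7 and rho = 0.3, and 68% at r = 0.8 and rho = 0.5. With the pre-session score added the figure is about 5% throughout. These are illustrations and not estimates for this trial. With imperfect reliability some bias remains after adjustment.

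Severity is minor. A reader might infer that the trial's main results are in doubt, but nothing here supports that: the analysis is exploratory and confined to one arm, and the randomised comparison and the feasibility and acceptability outcomes do not depend on it.

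**What to change.** In Statistical Analyses, Exploratory outcomes, state that each post-session self-efficacy score enters the model together with the pre-session score of the same measure. Raw pre-to-post change may be added as an optional sensitivity analysis, since its bias runs opposite to that of the adjusted form while reliability exceeds r. Where a measure has no pre-session score, replace the word progress with post-session level for that measure.

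The cost is a sentence, one degree of freedom (33 to 32 residual at n = 35) and a wider standard error, about 1.4 times at r = 0.7. No new data are needed if the pre-session scores are collected as the documents suggest. Power for this analysis may rise or fall, depending on whether movement or level is what relates to later change; a fall is the price of answering the question about progress that the plan poses.

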Participant Involvement in Study. For a flowchart of participant contact points please see attachment ‘SPYKids Points of Contact’ in Appendix D. After completing the online eligibility screener, those who are ineligible will also be automatically sent a compassionate email via REDCap informing them that they are not eligible, with a resource list of mental

health, crisis, and parenting resources. Contact information for the research team will also be included should they have any questions regarding eligibility. Participants who are eligible will be informed via REDCap and automatically sent to the pre-questionnaire. Participants will be screened using questions (e.g., “Are you currently on a waitlist for accessing services for your child?”). Please see Appendix C for REDCap the Eligibility Screener.

Quick Summary of Participant Contact Points if eligible (N=70):

1. Participants will read the main program consent form.
2. If they agree to consent, participants will begin the online pre-questionnaires.
3. Following the pre-questionnaires participants will be randomized to either SAU or SSI group via ID# using an online tool (randomizer.org) and will be notified via email of what group they have been randomized to.
4. Participants randomized to the SSI Group (n=35) will take part in the 90-minute SSI via telehealth, the post-questionnaires immediately post intervention and the 2 follow up questionnaires (2 weeks after the SSI and 3 months after the pre-questionnaire) to assess maintenance effects. Immediately following randomization, participants will be sent an email with an invitation to book a time for the SSI using Microsoft Bookings, a University of Manitoba App part of the Microsoft 365 suite of apps. Participants in this group will also receive a follow-up email from the clinical coach 1-week following the SSI.
5. Participants randomized to the SAU group (n=35) will receive services as usual on the SCCY waitlist, as well as receive a list of psychological and family support services. They will also participate in the eligibility screener, pre-questionnaires, the 2-week post questionnaires, and 3-month post follow-up questionnaires.

Further Details on Project Components:

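### The two descriptions of the follow-up schedule conflict and no survey is named for the primary change score; under the complete-case rule this also risks losing SSI non-attenders from one arm only

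*Combined protocol and SAP*

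**What the plan says.** All references are to the combined protocol and SAP.

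- **Quick Summary of Participant Contact Points, item 4 (SSI).** After randomization, "participants will be sent an email with an invitation to book a time for the SSI". The arm then completes an immediate post-session questionnaire and "the 2 follow up questionnaires (2 weeks after the SSI and 3 months after the pre-questionnaire").
- **Same list, item 5 (SAU).** This arm completes "the 2-week post questionnaires, and 3-month post follow-up questionnaires". No starting event is given for the 2-week survey.
- **Honorarium paragraph.** Both SSI follow-ups are dated from the session, at two weeks and three months. Both SAU follow-ups are dated from the pre-questionnaire, at one month and three months. The paragraph before it, on time commitment, gives SAU parents just two surveys after randomization.
- **Statistical Analyses, Primary outcome.** "The primary analyses will compare the change in child mental health symptom scores between (a) the SPYKids vs SAU group". The model is linear, adjusts for the pre-intervention score and child age, and is tested at the 0.05 level. No survey is named. On the later survey the section adds: "Secondary analyses will examine persistence of these effects at the 3-month-follow-up".
- **Statistical Analyses, General considerations.** "Complete-case methods will be used for planned analyses; however, sensitivity analyses may be used to examine the impacts of imputation on conclusions", and that only "should the usual assumptions appear to be met (MAR, missing at random, or MCAR, missing completely at random"). No analysis set is defined.
- **Aims and Hypotheses.** Child well-being is listed under Secondary Outcomes, although Statistical Analyses calls child mental health primary.

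**The concern.** The two schedules cannot both be programmed into the survey system. Whichever is used, the first SSI follow-up moves with the booking date. The SAU follow-up does not, at least under the Honorarium paragraph. A difference between arms in change score would then mix the effect of the session with a difference in elapsed time.

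The second issue follows from the first. Randomization precedes booking, so some SSI parents may never attend. Their first follow-up has no date in either paragraph. If they are not surveyed, a complete-case analysis omits them while keeping comparable SAU parents. The comparison is then no longer between the groups as randomized. Optional imputation under MAR would not repair this if non-attenders differ in ways the model does not capture.

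**Working it through.** **1. Schedules side by side**

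| Survey | Contact-point summary | Honorarium paragraph |
|---|---|---|
| SSI first follow-up | 2 weeks from session | 2 weeks from session |
| SSI second follow-up | 3 months from pre-questionnaire | 3 months from session |
| SAU first follow-up | 2 weeks, no anchor given | 1 month from pre-questionnaire |
| SAU second follow-up | 3 months, no anchor given | 3 months from pre-questionnaire |

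Two cells conflict outright: the anchor of the SSI second follow-up and the interval of the SAU first follow-up.

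**2. Which survey is primary?** SAU parents have two surveys after randomization. The 3-month survey is assigned to the secondary analysis. That leaves the first follow-up, whose SAU date is the one in conflict. This is an inference, because Statistical Analyses does not say so.

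**3. Timing.** Let B be the weeks from pre-questionnaire to session. The documents give no booking window, so B is assumed. One month is 365.25/12/7 = 4.35 weeks and three months is 13.04 weeks.

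- First SSI follow-up = B + 2.
- Gap to SAU = (B + 2) - 2 = B if SAU is at 2 weeks (counted from the pre-questionnaire, an assumption), or (B + 2) - 4.35 if SAU is at 1 month.
- SSI second follow-up = 13.04 (contact-point summary) or B + 13.04 (Honorarium).
- Spacing of the two SSI follow-ups under the contact-point summary = 13.04 - (B + 2) = 11.04 - B.

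| B (weeks) | SSI first follow-up (week) | Gap, SAU at 2 weeks | Gap, SAU at 1 month | SSI second follow-up (week), Honorarium | SSI spacing, contact-point summary (weeks) |
|---|---|---|---|---|---|
| 1 | 3 | +1 | -1.3 | 14 | 10 |
| 2 | 4 | +2 | -0.3 | 15 | 9 |
| 4 | 6 | +4 | +1.7 | 17 | 7 |
| 8 | 10 | +8 | +5.7 | 21 | 3 |

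Under the Honorarium dates the first follow-ups align only when B is about 2.3 weeks (4.35 - 2). Under the contact-point dates they align only when B = 0, and the two SSI surveys coincide at B of about 11.

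**4. Loss of non-attenders (illustration only).** Assume a share q of the 35 SSI parents is lost, that they would score d residual SD worse than those kept, that SAU has no such loss, that there is no true effect and that the test is two-sided.

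- Bias = q × d. With q = 0.20 and d = 0.5 this is 0.10 residual SD.
- SE = sqrt(1/28 + 1/35) = 0.254, so bias/SE = 0.394.
- Rejection probability = 1 - Φ(1.960 - 0.394) + Φ(-1.960 - 0.394) = 0.059 + 0.009 = 0.068.

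For q = 10/20/30/40% at d = 0.5, the bias is 0.05/0.10/0.15/0.20 SD and the normal approximation gives 5.5/6.8/8.8/11.2%. A simulation of 10,000 trials per setting, with whole parents and the baseline-adjusted linear model, gives 5.0/6.4/7.6/9.6%. With d = 0.2 the approximation gives 5.1-6.0%, and with d = 0.8 it gives 6.2-21.3%. The bias is nil if d = 0 or if SAU loses equally, and a negative d reverses its sign.

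**The case against.** The strongest objection is to the step from complete-case to one-arm loss. Complete-case is a rule about missing scores, not about attendance. Item 4 lists both follow-ups for everyone randomized to SSI, with no attendance condition. Under that item the 3-month survey has a date even for non-attenders. A reader might infer that the plan drops non-attenders or analyses only those who attended; no sentence says so. Appendices not available here may also settle it: "For a flowchart of participant contact points please see attachment" points to Appendix D, and Measures points to a table of questionnaires in Appendix C. This objection stands, so the loss is put here only as a risk at the first follow-up.

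A reader might also see a payment bias, since the first SSI gift card follows the post-session questionnaire and the first SAU card follows randomization. Both arms receive $25 after each of the two follow-ups, so this adds little and is not relied on.

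Dating SSI from the session has a rationale: it fixes time since treatment. That is a legitimate trade-off, but it gives SAU no matching date and does not explain why the two paragraphs differ.

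This is also a pilot whose main goals are feasibility and acceptability, and the Background figure of 3.9 of 16 sessions attended concerns multi-session care and gives no rate for one telehealth session. Both points limit the stakes. Neither removes the conflict in dates or the missing time point for a comparison that the plan tests at p=0.05.

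**Conclusion.** The conflict between the two schedules is certain, and so is the absence of a named survey for the primary change score in Statistical Analyses. Both should be fixed. Unequal timing between arms follows for most booking waits. At an assumed 4 weeks, SSI is measured about 1.7 or 4 weeks later than SAU, depending on the paragraph followed; the 4-week figure also assumes that the SAU 2-week survey runs from the pre-questionnaire.

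One-arm loss of non-attenders is plausible but inferred. The illustrative 0.10 SD bias and type I error of about 6-7% rest on an assumed 20% loss, an assumed 0.5 SD gap and no such loss from SAU. They are not an estimate for this trial. A reader might take the upper figure of 21% as a finding, but it needs 40% loss together with a 0.8 SD gap, and the documents support neither. The feasibility and acceptability results are largely unaffected.

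**What to change.** 1. Reconcile the contact-point summary and the Honorarium paragraph. Date both outcome follow-ups in both arms from one pre-session event (randomization or pre-questionnaire), with the same intervals. State the expected booking time and make the first interval long enough to cover it. Keep the immediate post-session questionnaire for the SSI-only exploratory analysis.
2. Send both follow-ups, with the existing $25 payment, to every randomized participant whether or not they attended.
3. Name in Statistical Analyses the survey that gives the primary change score.
4. Replace the complete-case sentence with wording such as: participants are analysed in the arm assigned regardless of attendance; the mixed models use all available scores; a sensitivity analysis will be done that applies a missing-not-at-random shift, over a stated range, to SSI non-attenders without a score.
5. Report by arm the numbers randomized and returning each survey, and for SSI the numbers booked and attended.

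The cost is low: wording changes, automated invitations to non-attenders and modest extra analysis. There are two limits. A survey dated from a pre-session event may fall close to or before a late-booked session. The primary model would still omit anyone without a score, so the main gain comes from surveying non-attenders and from the committed sensitivity analysis.
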